9.7. Data analysis

9.7.1. Analysis population

To provide valid effect estimates, the analysis population may differ from the population of women enrolled in the registry. The subset of registry participants included in the analysis will include women who:

- Have the minimum data required for determining inclusion/exclusion into one of the study cohorts
- Have sufficient data either submitted or confirmed by an HCP (i.e., an HCP must submit or confirm the data used to define the eligibility criteria)
- Have a diagnosis of moderate-to-severe AD
- Are prospectively enrolled (i.e., currently pregnant at enrollment)
- Are not exposed to teratogens or investigational medications during pregnancy
- Are not multiple gestation pregnancies for the analyses of preterm birth, SGA, and postnatal growth deficiency

Within each cohort, the baseline characteristics of those included in the analysis population will be compared with those excluded from the analysis population to evaluate potential differences between the population enrolled in the registry to the analysis population.

9.7.2. Primary analysis: Crude outcome proportions

Demographic and baseline characteristics will be summarized with descriptive statistics for each cohort. For each continuous variable, the number of observations, median, mean, standard deviation, minimum, and maximum for each cohort will be reported. For each categorical variable, the frequency and percentage in each category by cohort will be reported.

PFIZER CONFIDENTIAL Page 41 of 67 For each exposure group, the proportion of participants with the outcomes of interest will be calculated. The proportion with the outcomes of interest will be calculated as described in Table 6.

In the analysis of MCMs, participants will be classified into exposure groups (CIBINQO exposed or comparator group) based on exposure during the first trimester (i.e., the etiologically relevant window). For all other outcomes, exposure groups will be defined based on exposure at any point during pregnancy. The exposed group will consist of women exposed to CIBINQO during pregnancy. The unexposed comparator group (i.e., primary comparator group) will consist of women not exposed to CIBINQO during pregnancy.

Outcome	Numerator	Denominator				
Primary Outcome – Major Congenital Malformation (MCM)						
Primary analysis: among live births	Live births with confirmed (i.e., adjudicated) MCMs (excluding MCMs not associated with medication exposure) among women with pregnancy outcome data and, based on exposure classifications mea sured during the first trimester	Live births among women with pregnancy outcome data and, if applicable based on cohort, exposure during 1 st trimester				
Sensitivity analysis: among all pregnancy outcomes	Live births and fetal losses with confirmed MCMs (excluding MCMs not associated with medication exposure) a mong women with pregnancy outcome data and, if applicable based on cohort, exposure during first trimester	Live births and fetal losses among women with pregnancy outcome data and, if applicable based on cohort, exposure during 1 st trimester				
Secondary Outcomes						
Minor congenital malformations	Live births with minor congenital malformations among women with pregnancy outcome data	Live births among women with pregnancy outcome data				
Spontaneous abortion (SAB)	SABs among women with pregnancy outcome data who are enrolled (and exposed, if applicable based on cohort) prior to 20 gestational weeks	Women with pregnancy outcome data who are enrolled (and exposed, if a pplicable based on cohort) prior to 20 gestational weeks				
Stillbirth	Stillbirths a mong women with pregnancy outcome data	Women with pregnancy outcome data				
Elective termination	Elective terminations among women with pregnancy outcome data	Women with pregnancy outcome data				
Preterm birth	Singleton preterm live births without MCMs among women with pregnancy outcome data who are enrolled (and exposed, if applicable based on cohort) prior to 37 gestational weeks	Singleton live births without MCMs among women with pregnancy outcome data who are enrolled (and exposed, if a pplicable based on cohort) prior to 37 gestational weeks				

Table 6.Calculation of Outcome Proportion

Outcome	Numerator	Denominator
Small for gestational age (SGA)	Singleton live births without MCMs who are SGA among women with pregnancy outcome data	Singleton live births without MCMs with weight data a mong women with pregnancy outcome data
Postnatal growth deficiency (at 4 and 12 months)	Singleton infants without MCMs who were not born preterm or SGA with postnatal growth deficiency based on weight/length/head circumference among infants with weight/length/head circumference data at the time point	Singleton infants without MCMs who were not born preterm or SGA with weight/length/head circumference data at the time point
Infant developmental delay (at 4 and 12 months)	Infants without MCMs who were not born preterm with developmental deficiency in a particular category among infants with developmental milestone data for the category at the time point	Infants without MCMs who were not born preterm with developmental milestone data for the category at the time point

 Table 6.
 Calculation of Outcome Proportion

MCM = major congenital malformation; SAB = spontaneous abortion; SGA = small for gestational age.

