- Authorization for her HCP(s) to provide data to the registry
- Exposed cohort only: Must receive at least one dose of CIBINQO at any time during pregnancy (from the date of conception [DOC] to pregnancy outcome) or prior to pregnancy (within 1 day prior to the DOC).
- Comparator cohort only: Must have a diagnosis of moderate-to-severe AD at any time prior to pregnancy outcome.

Variables:

The exposed group will include women with moderate-to-severe AD who are exposed to CIBINQO during pregnancy. The primary comparator group will include women with moderate-to-severe AD who are unexposed to CIBINQO during pregnancy. If sample size permits, a secondary comparator group will include the subset of women with moderate-to-severe AD who are exposed to other chronic systemic treatments that are not JAK inhibitors (e.g., dupilumab) during pregnancy.

The outcomes of interest are MCM, minor congenital malformations, SAB, stillbirth, elective termination, SGA, preterm birth, postnatal growth deficiency, and infant developmental delay. Endpoint adjudication will be conducted for occurrences of MCM and minor congenital malformations.

Baseline characteristics collected at enrollment include maternal demographics, maternal prepregnancy anthropometrics, maternal obstetrical history, family history of congenital malformations, AD disease information, and baseline pregnancy information.

Data sources:

Data will be collected from enrolled pregnant women and HCPs. A virtual research coordination center (VRCC) will be used for data collection. Therefore, this study does not

involve site investigators (i.e., HCPs are not accountable for consenting and enrolling participants). Participants will be recruited from the US.

Study size:

The registry aims to enroll a minimum of 400 pregnant women (200 abrocitinib-exposed participants, 200 comparator participants) to estimate the proportion of the primary outcome, MCM, with meaningful confidence and precision.

Data analysis:

The analysis population may differ from the population of women enrolled in the registry. The subset of registry participants in the analysis will include women who:

- Have the minimum data required for determining inclusion/exclusion into one of the study cohorts
- Have sufficient data submitted or confirmed by an HCP
- Have a diagnosis of moderate-to-severe AD
- Are prospectively enrolled (i.e., currently pregnant at enrollment)

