9.3.2. Outcomes

Table 1 presents the definitions of the outcomes of interest. For outcomes not reported by the HCP, additional information on outcome ascertainment is provided. Safety events of special interest (SESI), such as major and minor congenital malformation events, will be adjudicated. Additional details on the adjudication process will be available in a separate Adjudication Charter.

Outcome	Definition	Ascertainment		

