Major congenital malformation (MCM)	An abnormality of body structure or function that is present at birth, is of prenatal origin (i.e., birth defect), has significant medical, social, or cosmetic consequences for the affected individual, and typically requires medical intervention (CDC, 2020)	 The registry defines and codes MCMs with criteria specified by the CDCMACDP (CDC, 2021). a) Exclusion criteria for analyses: To a void misattribution of the malfomation to the medication, MCMs not associated with medication exposure, such as chromosomal abnormalities, genetic syndromes, prematurity-related conditions in infants born at <36 gestational weeks (e.g., patent ductus a retriosus, patent foramen ovale, inguinal hernias, or undescended testes), and positional effects (e.g., hip dislocation due to breech position or abnormal skull shape due to crowding by multiple fetuses), will not be considered MCMs in the statistical analyses (Holmes & Westgate, 2011). b) Adjudication process: A panel of 2 independent experts in clinical genetics and neonatology, blinded to exposure, will review all MCMs reported to the registry and classify them using the CDC's MACDP system. Additionally, the birth defect evaluators will provide their opinions regarding the timing of the development of observed defects. If additional information is needed to aid in classification, the birth defect evaluators will request additional information using the targeted follow-up processoutlined in Section 9.4.1. These assessments will be recorded in the database. If there is a discrepancy, a third expert will independently review and code the case serving as tie breaker. These reviews will occur soon after the MCM is reported. Additional reviews will occur if new information is received for the case, as well as the possible temporal association between exposure (to CIBINQO or comparator product) and the development of observed defects. Additionally, the SAC will review all MCM cases reported to the registry and reach consensus on the coding of each case. The Sponsor will not be involved in any activities related to case review or adjudication. 		

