Minor congenital malformation	An anomaly or abnormality of body structure that is present at birth, is of prenatal origin (i.e., birth defect), poses no significant health problem in the neonatal period, and tends to have limited social or cosmetic consequences for the affected individual (CDC, 2020)	The registry defines and codes minor congenital malformations with criteria specified as defined by CDC (CDC, 2019). The same process for a djudicating MCMs will be used to a djudicate minor congenital malformations.		
Spontaneous a bortion (SAB)	An involuntary fetal loss or the expulsion of the products of conception occurring at <20 gestational weeks	Section 9.3.3 provides information on the methods used to calculate gestational age.		

Table 1. Outcome Definitions and Ascertainment

Outcome	Definition	Ascertainment
Stillbirth	As defined by the ACOG, an involuntary fetal loss occurring at ≥ 20 gestational weeks or, if gestational age is unknown, a fetus weighing ≥ 350 g(ACOG, 2020)	Section 9.3.3 provides information on the methods used to calculate gestational age.
Elective termination	A voluntary fetal loss or interruption of pregnancy that occurs for any reason, including but not limited to for the preservation of maternal health or due to fetal abnormalities	-
Preterm birth	A live birth occurring at <37 gestational weeks	Section 9.3.3 provides information on the methods used to calculate gestational age.
Small for gestational age (SGA)	Birthweight <10th percentile for sex and gestational age using standard growth charts for full and preterm live-born infants (Battaglia & Lubchenco, 1967)	For the determination of SGA, the registry will utilize the sex-specific international growth reference standards from the INTERGROWTH-21st for those born between 24 ^{0/7} and 42 ^{6/7} gestational weeks (Villar et al, 2014; Villar et al, 2016). The INTERGROWTH-21st standards are the latest a vailable global reference standards, representing contemporary information from an international, multiethnic, diverse population, and have been specifically developed for modern research.

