As the registry will enroll women only after recognition of pregnancy and in some cases may be much later in pregnancy, there will be left truncation of the enrolled population. That is, the enrolled population of pregnant women will include women with a shortened period at risk of the outcomes of interest and exclude women who have already had certain outcomes (e.g., SAB, elective termination). To minimize the impact of this potential bias, statistical methods may be used to address left truncation, and the registry's recruitment strategy will encourage recruitment of participants as early in pregnancy as possible.

Additionally, women in the exposed cohort may differ from those in the comparator cohort in important factors that could impact pregnancy outcomes. For example, patients who seek and receive CIBINQO for moderate-to-severe AD may have more severe disease than the comparator patients, so confounding by indication will need to be carefully considered for the comparison. Furthermore, there may be misclassification of disease severity, particularly in the comparator cohort, as use of chronic systemic therapies for AD will be used as a proxy for moderate-to-severe disease. Standardized methods for assessing AD severity are not available and severity is not routinely documented in medical records.

To minimize the impact of potential confounders, the registry will record the characteristics of women in both cohorts and use statistical methods to examine and account for any differences between cohorts in the analysis. The registry will employ identical data collection and follow-up procedures across the registry cohorts to minimize any potential recording/detection bias. Although statistical methods will be used to account for confounding, it may not be possible to control for all variables (e.g., unknown) that could influence the results of the study. Therefore, residual confounding remains a possibility.

Outcome misclassification is possible, especially with regard to minor congenital malformations that may be overlooked or unreported. Although some MCMs may not be easily visible at birth, most will be apparent by 12 months of age, so misclassification of these outcomes is expected to be minimal in this registry.

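### Defects with causes unrelated to medication are excluded for major malformations only, so minor malformations from the same causes count as events (Protocol Tables 1 and 6)

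*Protocol*

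**What the plan says.** Section 9.3.2, Table 1, has two separate items in the MCM row. Item (a) lists causes that do not count as MCMs in the statistical analysis: chromosomal, genetic-syndrome, prematurity-related and positional. The stated purpose is to keep a defect with another cause from being attributed to the drug. Item (b) describes adjudication: "A panel of 2 independent experts in clinical genetics and neonatology, blinded to exposure, will review all MCMs reported to the registry".

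The minor-malformation row of Table 1 refers to a CDC list for coding and then says "The same process for a djudicating MCMs will be used to a djudicate minor congenital malformations". It does not mention item (a).

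Section 9.7.2, Table 6, defines the primary MCM numerator as "Live births with confirmed (i.e., adjudicated) MCMs (excluding MCMs not associated with medication exposure) among women with pregnancy outcome data". The MCM sensitivity row also carries the confirmation requirement and the exclusion. The minor-malformation numerator reads "Live births with minor congenital malformations among women with pregnancy outcome data", with neither condition.

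Adjudication of minor malformations is nevertheless stated in several places. The abstract says "Endpoint adjudication will be conducted for occurrences of MCM and minor congenital malformations". Section 9.3.2 says "Safety events of special interest (SESI), such as major and minor congenital malformation events, will be adjudicated". Section 11 assigns both outcomes to the endpoint committee.

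**The concern.** The reason given for item (a) applies to minor anomalies as much as to major ones. A minor anomaly that is part of a chromosomal syndrome, or that results from prematurity or fetal position, tells the reader nothing about the drug. Under the present wording it still enters two results. One is the crude proportion in each cohort, which is the primary objective (section 8). The other is the crude and adjusted RR that section 9.7.3 plans for every outcome where event numbers allow.

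In a safety registry the usual consequence is attenuation: a real increase in minor malformations looks smaller than it is. The two malformation outcomes would also be reported side by side on different case definitions, and nothing in the tables tells the reader so.

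**Working it through.** **Comparison of the text**

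| Element | MCM | Minor malformation |
|---|---|---|
| Table 1, item (a): causes excluded from analysis | Stated | Not stated |
| Table 1, item (b): adjudication blinded to exposure | Stated | Carried over by reference |
| Table 6: confirmed cases only | Stated in both rows | Not stated |
| Table 6: exclusion of causes unrelated to medication | Stated in both rows | Not stated |

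The Table 1 cross-reference carries over the adjudication process, which is item (b). Item (a) is a separate analysis rule worded for MCMs. The adjudication gap in Table 6 is therefore filled by other parts of the protocol, but the exclusion gap is not.

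**A figure to reproduce**

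There is none. Minor malformations have no row in Tables 3, 4 or 5, and the protocol gives no prevalence for them.

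**Size of the effect on the RR**

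Inputs, all assumed because the protocol gives none:
- p is the risk of any minor malformation in the unexposed cohort.
- f is the share of those unexposed-cohort cases due to the item (a) causes.
- The absolute risk from those causes, f × p, is the same in both cohorts.
- RR is the true relative risk for the remaining cases.

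Unexposed risk: (1−f)p + fp = p.
Exposed risk: RR × (1−f)p + fp.
Observed RR = exposed / unexposed = (1−f) × RR + f.

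| f | True RR 3 | True RR 2 |
|---|---|---|
| 10% | 0.9×3 + 0.1 = 2.8 | 0.9×2 + 0.1 = 1.9 |
| 20% | 0.8×3 + 0.2 = 2.6 | 0.8×2 + 0.2 = 1.8 |
| 30% | 0.7×3 + 0.3 = 2.4 | 0.7×2 + 0.3 = 1.7 |
| 40% | 0.6×3 + 0.4 = 2.2 | 0.6×2 + 0.4 = 1.6 |

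Two properties of the formula matter:
- With a true RR of 1 the observed RR is (1−f) + f = 1, so under equal absolute risk no false signal arises.
- f must be defined on unexposed cases. If the excluded causes made up the same share f of cases in each cohort, both risks would shrink by the factor (1−f) on exclusion and the RR would not change.

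**Size of the effect on the crude proportion**

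The unexposed proportion is p where it would be (1−f)p with the exclusion, a ratio of 1/(1−f). That is 1/0.9 = 1.11 at f = 10% and 1/0.6 = 1.67 at f = 40%.

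**The case against.** The strongest reply is that Tables 1 and 6 agree with each other on the exclusion: both restrict it to MCMs, so it may be a deliberate choice. How many anomalies on the CDC minor list could be chromosomal, prematurity-related or positional depends on that list and on the separate Adjudication Charter, neither of which is available here. The outcome is secondary, has no sample-size row, and is compared only if numbers allow. This stands in part. It limits the weight of the point and leaves the 10% to 40% range as illustration only. It does not explain why the rationale in item (a) should stop at major defects, and the protocol gives no reason.

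A reader might also infer from the bare Table 6 row that every reported minor malformation is counted, including unscreened reports from providers who know the exposure. The documents do not support that. The row does not say reported, and the protocol commits repeatedly to adjudicating minor malformations, by the same panel blinded to exposure. Other Table 6 rows (preterm birth, SGA, postnatal growth, development) refer to infants without MCMs and also omit the word confirmed, so its absence is weak evidence that adjudication is ignored.

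Nor should the point be stretched to differential reporting. Section 9.9 acknowledges "minor congenital malformations that may be overlooked or unreported", but adjudication sees only cases that reach the registry. It cannot correct unequal completeness between cohorts, and the same limitation applies to MCMs.

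**Conclusion.** The point holds as a gap in the exclusion rule. Minor malformations due to causes that the protocol treats as unrelated to medication count as events, while major malformations from those causes do not. For an assumed f of 10% to 40%, the observed RR falls to 2.8 to 2.2 when the true RR is 3, and to 1.9 to 1.6 when it is 2. This requires f to be measured among unexposed cases and the absolute risk from these causes to be equal in the two cohorts. If that risk differs between cohorts, the distortion could go either way.

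The missing confirmation wording in the Table 6 row is only an inconsistency with Table 1 and should be aligned. It does not show that adjudication is absent or unused. Overall this is a cheap improvement to a secondary outcome.

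**What to change.** 1. In Table 1, state that item (a) also applies to minor congenital malformations. If the restriction to MCMs is intended, say so and give the reason.
2. In Table 6, reword the minor-malformation numerator so that it counts live births with a confirmed (adjudicated) minor congenital malformation and leaves out those not associated with medication exposure, in parallel with the MCM row.
3. List the excluded minor malformations separately by cohort and cause, so that nothing is lost from view.

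The cost is a few words in two tables and one listing. Adjudication of these cases is already planned. The downside is a slightly smaller event count, and so slightly less precision for this outcome.

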^c Participants may be retrospectively enrolled into the registry up to one year after pregnancy outcome but will not be included in primary analysis.

The data collection process for each participant following routine care will begin at enrollment, and data throughout the pregnancy will be collected at 3 time points: at enrollment, at the end of the second trimester (approximately 26 gestational weeks), and at pregnancy outcome (live birth or fetal loss). For women who enroll after the second trimester, data during pregnancy will be collected at enrollment and at pregnancy outcome. For live-born infants, data from pediatric visits at 4 and 12 months of age will be collected at 2 time points: 4 months and 12 months after delivery. A participant will be considered lost to follow-up if follow-up information is never obtained or is unavailable after the attempts outlined in Section 9.4.1. Pregnant women without pregnancy outcome information will be considered lost to follow-up, and live-born infants without any follow-up data after birth will be considered lost to follow-up.

Data collection efforts will be identical for all enrolled pregnant women regardless of their exposures and study cohort assignment. HCPs who serve as reporters to the registry will be instructed to transcribe data that are readily available in the participants' medical records into the data collection forms. Electronic and paper data collection forms will be used in this study. These data collection forms can be submitted on paper, via email/fax, or via phone.

At enrollment, once consent, registration information (including eligibility criteria), reporter contact information, and medical releases have been provided by the pregnant woman, maternal demographic characteristics and pre-pregnancy anthropometrics will be collected from the pregnant woman. These data will be collected on the *Registration Form for Participants*. Registration information, including eligibility criteria, will be confirmed by HCP(s), as appropriate. The HCP(s) will additionally provide maternal obstetrical history, family history of congenital malformations, disease information, pregnancy information, and

PFIZER CONFIDENTIAL Page 19 of 67

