maternal exposures during pregnancy. All of these data will be collected on the *Registration Form for Healthcare Providers* and *Pregnancy Information Form*. At approximately the end of the second trimester, the HCP(s) will be asked to complete another *Pregnancy* Information Form, which will collect any updates to pregnancy information and maternal exposures during pregnancy. Around or after the estimated date of delivery (EDD) or after a known pregnancy outcome, the HCP(s) will be asked to complete another *Pregnancy* Information Form as well as the **Pregnancy Outcome Form**, which will collect pregnancy outcome information. For each live-born infant, the pediatric HCP will be asked to complete an Infant Outcomes Form, which will collect infant information, including infant growth and development data, at 2 time points: at approximately 4 and 12 months after delivery. These visits are part of the American Academy of Pediatrics' recommended infant well-child visit schedule (American Academy of Pediatrics, 2021). If a congenital malformation (major or minor) or other event of interest is reported, additional information may be requested from the reporting HCP on the *Targeted Follow-up Form* to properly characterize the event. The date each data collection form is completed also will be collected. Additional details on the data collected are available in Section 9.4.

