- Concurrent pregnancy-related maternal medical conditions or pregnancy complications, including
 - Pregnancy-induced hypertension
 - Pre-eclampsia
 - o Eclampsia
 - Gestational diabetes
 - Preterm labor
 - Placenta previa
 - Placental abruption
 - Incompetent cervix
 - Ectopic pregnancy
 - Molar pregnancy

Maternal Exposures During Pregnancy (reported by the obstetric and/or prescribing HCP)

- Exposure to CIBINQO, including indication/reason for use (FDA-approved or offlabel), dose, route, frequency, and dates/duration of exposure, if available
- Exposure to other drugs or biological products (including prescription and non-prescription drugs, dietary supplements, vaccines, known teratogens, and investigational medications), including indication/reason for use, dose, route, frequency, and dates/duration of exposure, if available
- Exposure to tobacco, alcohol, marijuana, or recreational or illicit drugs, including timing of exposure, if available

Pregnancy Outcome Information (reported by the obstetric and/or pediatric HCP)

- Pregnancy outcome (for each fetus, classified in one of the following mutually exclusive categories: SAB, stillbirth, elective termination, and live birth)
- Date of pregnancy outcome
- Gestational age at pregnancy outcome
- Fetal/infant sex
- Fetal/infant weight, length, and head circumference at pregnancy outcome

PFIZER CONFIDENTIAL Page 32 of 67

- Route of delivery (i.e., spontaneous vaginal delivery, assisted vaginal delivery, or cesarean delivery)
- 5-minute Apgar score
- Congenital malformations (major and minor) and assessment of potential contributing factors
- For a non-induced fetal loss (SAB, stillbirth), factors that may have had an impact on the fetal loss and attribution
- For elective termination, reason (e.g., finding on prenatal test, risk to mother's health, undesired pregnancy)
- Maternal weight at (just prior to) pregnancy outcome

Infant Outcome Information (reported by the pediatric HCP)

- Infant weight, length, and head circumference at birth (if not provided at pregnancy outcome) and at 4 and 12 months of age
- Achievement of the developmental milestones in each Centers for Disease Control and Prevention (CDC)-defined category (social/emotional, language/communication, cognitive, and movement/physical development) at 4 and 12 months of age
- Congenital malformations (major and minor) and assessment of potential contributing factors
- Infant death, including date and cause of death

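### The Table 6 denominator for spontaneous abortion (SAB) drops women already known not to have had a SAB

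*Protocol*

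**What the plan says.** - **Definition.** Protocol Section 9.3.2, Table 1, defines SAB as "An involuntary fetal loss or the expulsion of the products of conception occurring at <20 gestational weeks". Nothing after 20 0/7 weeks can change a woman's SAB status.
- **Counting rule.** Section 9.7.2, Table 6, gives the numerator as "SABs among women with pregnancy outcome data who are enrolled (and exposed, if applicable based on cohort) prior to 20 gestational weeks". The denominator carries the same restriction to "women with pregnancy outcome data who are enrolled" before 20 weeks.
- **What is an outcome.** Section 9.4 has each fetus "classified in one of the following mutually exclusive categories: SAB, stillbirth, elective termination, and live birth". A continuing pregnancy is not on that list.
- **Women without an outcome.** Section 9.2: "Pregnant women without pregnancy outcome information will be considered lost to follow-up".
- **Contact after the SAB window.** Section 9.2 schedules a data collection point at about 26 gestational weeks. The HCP completes another Pregnancy Information Form then, "which will collect any updates to pregnancy information and maternal exposures during pregnancy".

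No provision lets the 26-week report stand as evidence that a SAB did not occur.

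**The concern.** The 20-week limit in the SAB row governs entry (enrolled, and exposed where relevant, before 20 weeks) but not ascertainment. To be counted as a non-case, a woman needs a recorded stillbirth, elective termination or live birth. Her 26-week form does not count, although it already answers the SAB question.

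Other rows of Table 6 match the denominator to the data that the outcome needs: birth weight for small for gestational age, and measurements at the time point for growth and development. The SAB row does not.

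The crude SAB proportion falls under the primary objective, although Table 6 lists SAB among the secondary outcomes. It is also reported from a postmarketing safety requirement. The rule discards information that the registry holds, and every woman it discards in this way is a non-case.

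**Working it through.** **Inputs**
- Reference SAB prevalence p = 11.8% (Section 9.5.2, Table 3).
- Precision is the Wilson 95% half-width (Section 9.5.2).
- Section 9.5.2 allows 10% for all exclusions together, including loss to follow-up. No separate figure for loss is given.
- L is the share of women without a SAB who are documented as pregnant at or after 20 weeks and have no later outcome. This is an assumption.
- s is the share of SABs that never reach the registry. This is an assumption.

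**1. The plan's own figure.** The half-width is z·√(p(1−p)/n + z²/4n²) / (1 + z²/n), with z = 1.96. At p = 0.118 and n = 446:
- p(1−p)/n = 0.104076/446 = 0.0002334
- z²/4n² = 0.0000048
- half-width = 1.96 × √0.0002382 / 1.0086 = 0.0300

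This is the ±3% that Table 3 shows for 446 women. The other SAB entries in Table 3 reproduce as well, so the issue is the denominator rule and not the arithmetic. At n = 200 the half-width is 0.0449. At 180 (200 × 0.9) it is 0.0473.

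**2. Direction for the affected women.** With x SABs among N women, dropping k known non-cases changes x/N to x/(N − k), which is larger for any k > 0.

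**3. Size if every SAB is ascertained (s = 0).** Observed proportion = p / [p + (1 − p)(1 − L)].

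| L | Calculation | Observed | Shift (points) |
|---|---|---|---|
| 2% | 0.118 / (0.118 + 0.882 × 0.98) | 12.0% | +0.2 |
| 5% | 0.118 / (0.118 + 0.882 × 0.95) | 12.3% | +0.5 |
| 10% | 0.118 / (0.118 + 0.882 × 0.90) | 12.9% | +1.1 |

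The 10% row is an upper reading, because it gives the whole exclusion allowance to loss after 20 weeks. In counts, 200 women contain 23.6 expected SABs and 176.4 non-cases. Late loss of 5% removes 8.8 non-cases, and 23.6/191.2 = 12.3%.

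**4. Net effect when some SABs are missed.** Observed proportion = p(1 − s) / [p(1 − s) + (1 − p)(1 − L)].
- L = 10%, s = 10%: 11.8%, no net bias.
- L = 10%, s = 15%: 0.1003 / (0.1003 + 0.7938) = 11.2%, a net downward bias.

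**5. Relative risk with no drug effect and s = 0.**
- Late loss of 10% in both cohorts: 12.9/12.9 = 1.00.
- Late loss of 10% in one cohort and 5% in the other: 0.1294/0.1234 = 1.05, or 0.95 the other way round.

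**The case against.** The strongest reply is that the effect is small, its net sign is not fixed, and the protocol works to limit loss.

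- **Loss is actively limited.** Section 9.4.1 sets an initial request, three further attempts and a certified letter. Under Section 9.2.3.2, HCPs caring for the pregnant woman are paid only once outcome data are collected. Section 9.7.1 compares the baseline characteristics of included and excluded women, and Section 9.9 admits that outcomes in those lost could differ. These measures reduce or describe loss. They do not change how a woman with a 26-week form is counted. Censoring weights appear only as an option (Sections 9.7.4 and 9.9) and leave the crude proportion in Table 6 as it is.
- **A reader might infer that the reported SAB proportion must be too high.** The documents do not support that. The sign is certain only for women with a documented continuing pregnancy, and step 4 shows that unreported SABs can cancel or reverse the total. Unreported SABs are a separate problem and no reason to drop known non-cases. The late entry discussed in Section 9.9 is separate too. The upward shift here is relative to women enrolled before 20 weeks, not to all pregnancies.
- **A reader might infer that every non-case must be followed to term while every SAB is complete before 20 weeks.** Terminations, stillbirths and preterm births all count as outcomes, and a SAB may first come to light at the 26-week contact or around the due date.
- **A reader might infer a biased relative risk.** That needs late loss to differ between cohorts. Section 9.2 makes data collection identical across cohorts, and nothing in the protocol points to a difference.
- **The 26-week form may not record that the pregnancy continues.** This stands in part. Section 9.4 lists pregnancy status only under registration, so a continuing pregnancy would have to be derived from the dated form or captured in a new field.

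**Conclusion.** The point holds in a limited form. As written, Table 6 removes known SAB non-cases from the denominator, and for those women the crude proportion can only rise. The shift is about 0.2 to 0.5 points at 2% to 5% late loss and 1.1 points at the 10% upper reading. This assumes a true SAB proportion of 11.8%, all SABs ascertained, and late loss rates that the protocol does not give. The shift is well inside the half-width of about 4.5 points at 200 women, but more enrolment would not remove it.

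It does not follow that the overall SAB estimate is biased upward or that the comparison between cohorts is distorted. The first also depends on unreported SABs, the second on unequal late loss. This is an inexpensive improvement to a stated rule and does not by itself threaten the study's conclusions.

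**What to change.** Define the Table 6 SAB denominator as women enrolled (and exposed, if applicable) before 20 gestational weeks who have either pregnancy outcome data or an HCP-documented continuing pregnancy at or after 20 0/7 weeks. Count the latter as non-cases, and apply the same population to the numerator. Women last known to be pregnant before 20 weeks stay in the missing group.

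The cost is one line in Table 6 and the matching line in the SAP. Continuing-pregnancy status can be derived from the dated end-of-second-trimester form or recorded in one explicit field on it. No additional contact with participants or HCPs is needed.
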